## **2 STUDY OBJECTIVES**

### **2.1 Primary Objective**

Improvement of lupus inflammatory polyarthritis measured by proportion of patients who achieve >=20% improvement in tender and swollen 28 joint counts at 16 weeks.

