**Study follow up phone call, 8 weeks after last study dose (Week 24)**

The study coordinator will conduct a follow up phone call 8 weeks after subject's last study visit (week 24) to ask about any Adverse Events. At minimum two attempts should be made to contact the subjects if subject is not available upon first contact.

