- d. Joint ultrasound done at Baseline and Week 16 (visit 5)
- e. Study subjects should stay at the study site for 1 hour following the administration of the first dose for assessment of signs and symptoms of adverse reactions
- f. Done at Baseline and 16 weeks (Visit 5) only.

- h. Dispense study drug and review compliance and accountability. Instruct subjects to complete the dosing diary
- i. A follow up phone call at Week 24 (8 weeks after subject's last study visit) should be conducted to ask about any Adverse Events and Concomitant Medication. At minimum, two attempts should be made to contact the subject if the subject is not available upon first contact.

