#### **6.4.1 Primary Efficacy Assessment**

1. Proportion of patients who achieve  $\geq 20\%$  Improvement in tender and swollen joint counts at 16 weeks

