### ***8.4.3 Efficacy Analyses***

The Fisher's exact test will be used to compare the percent of subjects achieving primary and secondary outcomes between two groups. Wilcoxon rank sum tests will be used to compare ordinal and quantitative outcomes between groups. Logistic regression will also be used to adjust for baseline clinical presentation and demographic factors. A site by treatment interaction effects will be included in the model to account for possible differences in treatment efficacy between our two sites. Bivariate analysis and nonparametric analysis (for example local polynomial regression or generalized additive model analysis) will be carried out to inspect the relationship between outcome and covariates. The goodness-of-fit of logistic models will be evaluated using the Hosmer-Lemeshow test. With the quantitative outcomes such as joint counts, ultrasound measurements, etc we will use Poisson regression to assess the treatment effect or linear regression for continuous outcomes. Poisson regression is a special case of generalized linear model and robust pseudo likelihood inference will be used in the analysis. We also will use multiple imputation technique to accommodate possible missing data at 12 and 24 weeks due to patients lost to follow up. The imputation model will include all baseline 12 week and 24 week outcomes and covariates to impute the missing outcomes . Analyses will be done with and without imputation.

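### The multiple-imputation rule names weeks 12 and 24 although the primary endpoint is at week 16, and neither the imputed nor the non-imputed analysis is named as primary

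*Combined protocol and SAP*

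**What the plan says.** The primary objective (Section 2.1) is the proportion of patients with at least 20% "improvement in tender and swollen 28 joint counts at 16 weeks", and Section 6.4.1 repeats the week-16 time point. Treatment and efficacy visits end at week 16 (Section 4.1 and the visit lists in Section 6.1).

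Section 8.4.3 says Fisher's "exact test will be used to compare the percent of subjects achieving primary and secondary outcomes between two groups". On missing data it proposes a "multiple imputation technique to accommodate possible missing data at 12 and 24 weeks due to patients lost to follow up", and then: "The imputation model will include all baseline 12 week and 24 week outcomes and covariates to impute the missing outcomes". Week 16 is not named anywhere in the section. It closes with "Analyses will be done with and without imputation" and does not say which result carries the primary conclusion.

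Week 24 is a telephone follow-up. Footnote i of the Time and Events Schedule says that the call "should be conducted to ask about any Adverse Events and Concomitant Medication". The schedule table places no joint count or other efficacy measure in that column.

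Section 8.2 analyses the 64 enrolled patients. Section 8.1 sizes the trial on 56 completers, and the synopsis expects 30 completers per group, which is 60.

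**The concern.** An imputation rule should target the outcome it protects. This one names week 12, which is a real visit but not the primary time point, and week 24, where no efficacy outcome is collected. A programmer following it literally would impute nothing at week 16 and would look for week-24 outcomes that are not in the database.

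The second gap is the missing ranking. A patient with no week-16 count can enter Fisher's test on 64 patients only if some rule assigns a response, and none is given for loss to follow-up. The analysis without imputation could therefore mean completers only, or all 64 with an unstated rule. If this is settled after unblinding, it becomes a choice between results.

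The plan itself expects about 4 to 8 patients not to complete. Some of that loss may be related to response, because Section 4.2.3 has the investigator consider discontinuing a patient whose disease is significantly worse at week 8.

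**Working it through.** **Time points side by side**

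| Week | Joint count scheduled | Role in Section 8.4.3 |
|---|---|---|
| 0 | yes | in the model |
| 4, 8 | yes | not named |
| 12 | yes | imputed, and in the model |
| 16 (primary) | yes | not named |
| 24 | no (telephone call) | imputed, and in the model |
| Early withdrawal | yes | not named |

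**The plan's own figures.** Inputs from Section 8.1 are 67% v 30%, alpha 0.05 (two-sided assumed) and power 0.80. With a mean rate of 0.485:

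n = [1.960·√(2·0.485·0.515) + 0.842·√(0.67·0.33 + 0.30·0.70)]² / 0.37² = 27.4, so 28 per group.

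Dropout is 35%/3 = 11.7%, about 12%. Then 28/0.88 = 31.8, so 32 per group, and 64 × 0.88 = 56.3 completers. The plan's figures reproduce. About 8 patients are missing by Section 8.1, or 64 − 60 = 4 by the synopsis.

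**Completers versus imputed (the two analyses the plan states).** The counts are assumed. Missing responses are drawn within each arm from a beta posterior with Jeffreys prior, so the filled rate is [x + m(x + 0.5)/(n + 1)]/32, for x responders among n observed and m missing. For example, 17/27 gives [17 + 5·17.5/28]/32 = 62.9%.

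| Assumed counts (abatacept v placebo) | Completers, points | Imputed, points (95% CI) | Missing = non-response, points | Fisher p: completers; non-response |
|---|---|---|---|---|
| 19/28 v 8/28 | 39.3 | 39.1 (14.5 to 63.7) | 34.4 | 0.007; 0.011 |
| 20/30 v 9/30 | 36.7 | 36.6 (12.6 to 60.6) | 34.4 | 0.009; 0.011 |
| 17/27 v 9/29 | 31.9 | 31.8 (6.5 to 57.1) | 25.0 | 0.031; 0.074 |

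Completers and imputed estimates differ by 0.1 to 0.2 points and agree on significance in all three rows. The only change of significance is between completers and non-response, in the third row.

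**Completers versus missing-as-non-response.** This is an exact enumeration of two-sided Fisher tests at 67% v 30%, with missingness assumed unrelated to response.

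| Missing (abatacept v placebo) | Power, completers | Power, non-response | Opposite sides of 0.05 |
|---|---|---|---|
| 2 v 2 | 76.8% | 76.8% | 0.0% |
| 4 v 4 | 71.3% | 70.9% | 0.4% |
| 5 v 3 | 74.6% | 60.9% | 13.7% |
| 3 v 5 | 75.7% | 79.5% | 3.8% |

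These are exact Fisher powers, so they sit below the plan's 0.80, which comes from the uncorrected normal formula above.

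To average over splits, weight each by C(32,k)·C(32,T−k)/C(64,T), where k of T missing patients fall in the abatacept arm. For T = 4 and k = 0 to 4, the weights are 0.057, 0.250, 0.387, 0.250 and 0.057, and the disagreements are 9.9%, 3.2%, 0.0%, 11.7% and 21.1%. The weighted sum is 5.5%. The same calculation for T = 8 gives 9.1%.

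**The case against.** The strongest reply is that this is leftover wording. Section 5.5.1 refers to a 24-week study period, and the early-withdrawal text in Section 6.1 points to a Visit 7 at week 24 that the schedule does not contain. The second imputation sentence says only that missing outcomes are imputed, so a sensible analyst would include week 16. That is a likely explanation, but it does not correct the operative text, and relabelling the weeks would still leave the two analyses unranked.

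The documents also deal with part of the informative dropout. Section 4.1 classes certain steroid and background-therapy changes as treatment failure and calls early leavers back within a week, and the schedule table places a joint count at that visit. These provisions help, but they do not classify every patient lost to follow-up.

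On size, a reader might infer that the open choice between the plan's two stated analyses can decide significance. The documents and the calculations do not support that. Every change of significance shown involves counting missing as non-response, a rule Section 8.4.3 never states. It enters only as one possible reading of the 64 patients in Section 8.2. The imputation checked uses treatment arm alone, not the covariates and outcomes the plan would include, so it says little about how far the planned model could move the result. The 13.7% is also conditional on a 5 v 3 split.

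A reader might also infer that non-response counting must be primary. That is a debatable trade-off: it costs almost nothing with equal dropout, but power is 60.9% against 74.6% with 5 v 3 missing.

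**Conclusion.** The point holds in a limited form. As written, the missing-data rule omits the primary time point and names one with no efficacy data, and the plan does not say which analysis is primary or what the analysis without imputation does with a missing week-16 count.

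The measurable consequence is for completers versus missing-as-non-response. Disagreement at 0.05 is negligible with equal dropout (0.4% at 4 v 4) and 13.7% at 5 v 3. It is about 9% overall with 8 missing at random, or 5.5% with 4. These figures assume the plan's 67% v 30% and missingness unrelated to response. For imputed versus completers, no change of significance has been shown.

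This should be fixed before unblinding. It does not put the design or the sample size in doubt. The synopsis (inclusion criteria) and Section 4.1 also word their treatment-failure rules differently. That is a separate point, and those passages should be reconciled.

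**What to change.** In Section 8.4.3:

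1. Replace weeks 12 and 24 with week 16 as the imputation target, and delete week-24 outcomes from the model.
2. Impute the week-16 joint counts from treatment arm, baseline count and the collected post-baseline counts (weeks 4, 8, 12 and any early-withdrawal count), then derive response from the imputed counts.
3. Before unblinding, name one primary analysis of the 64 randomised patients and state how a patient without a week-16 count is classified in the analysis without imputation. The other analysis becomes the sensitivity analysis. Non-response counting is one option and keeps Fisher's test simple, but it is not the required one.
4. State how imputed results are pooled, for example a risk difference or logistic regression under Rubin's rules. Compare the two analyses on the risk difference and its interval, not on p-values from different tests: 17/32 v 9/32 gives Fisher p = 0.074 but Wald p = 0.035 on the same data.

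The cost is wording only, with no new visits or patients. If non-response counting is chosen, like-for-like power hardly changes with equal dropout (70.9% v 71.3% at 4 v 4; 76.8% for both at 2 v 2). The cost is larger when more abatacept than placebo patients are missing, so the corrected imputation should be kept beside it.

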Study Design:	Randomized trial of 32 SLE patients treated with subcutaneous abatacept 125mg sq once a week vs. 32 placebo treated subjects over a 16 week period. Patients will be seen every 4 weeks from baseline. One half of patients will be recruited at UCLA and one-half at UCSD. We expect 30 patients in each group to complete the 16 week study.
Study Schema Drugs / Doses / Length of Treatment)	Abatacept 125 mg or placebo will be administered subcutaneously once a week for 16 weeks. There will be a telephone follow up 2 months after the last injection to capture post-treatment adverse events.
Accrual Goal: (Total number of subjects)	64 (32 at UCLA and 32 at UCSD)
Accrual Rate: (Number of subjects expected per month)	2-3 subjects per month at each site
FPFV: April 1, 2015 LPFV: March 31, 2018  Follow Up: 16 weeks per patient plus 8 weeks of observation for adverse events	
Correlative Studies: These will be performed at the UCLA site only	
1) Biomarkers: a) T cell numbers and phenotypic and functional characteristic in PBMC measured at week 0 and 16. These will include for T cells CD4+, CD3+, CD25+, CD8+, Foxp3+ and cytoplasmic stains for IFNgamma, IL2, IL-17, IL21 and IL-10.
 
b) B cell numbers and subsets, including naïve, activated and plasmablasts.
 
c) Ability of autologous CD4+CD25hi T cells to suppress proliferation of CD4+CD25- T cells.
 
d) Cytokines in serum: IFNgamma, IL-6, IL-10, IL-17, IL23 and BLyS
 
2) Ultrasound with power Doppler of joints assessing synovitis, tenosynovitis (18 joints) and erosions at week 0 and 16.

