#### **4.2.3 Discontinuation of Subjects from Treatment**

If a study subject is found to have worsening disease activity during the duration of the study, the choice of using a rescue medication (e.g. increase prednisone dose but not to  $>20$  mg daily) will be considered. However, if significant worsening of disease activity is found at 8 weeks in comparison to baseline disease activity, the investigator will consider the discontinuation of the subject from the study after discussing in detail with the patient alternative SLE treatment strategies. Throughout the duration of the study, background allowed standard of care therapies (prednisone, MMF, leflunomide, hydroxychloroquine) will be continued at the baseline dosage.

Subjects MUST discontinue study treatment and withdraw from the study for any of the following reasons:

- Withdrawal of informed consent (subject's decision to withdraw for any reason)
- Any clinical adverse event (AE), laboratory abnormality, or intercurrent illness which, in the opinion of the investigator, indicates that continued participation in the study is not in the best interest of the subject
- Pregnancy
  - Instruct WOCBP to contact the investigator or study staff immediately if they suspect they might be pregnant (eg, missed or late menstrual period) at any time during study participation. Institutional policy and local regulations should determine the frequency of on-study pregnancy tests for WOCBP enrolled in the study.
  - The investigator must immediately notify BMS if a study subject becomes pregnant. The mechanism for reporting pregnancy is described in Section 7.6.
- Termination of the study by BMS
- Loss of ability to freely provide consent through imprisonment or involuntarily incarceration for treatment of either a psychiatric or physical (eg, infectious disease) illness

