#### **6.4.2 Secondary Efficacy Assessments**

1. Changes in synovitis, tenosynovitis and erosions measured by high-energy ultrasound with Doppler flow at Baseline and 16 weeks.
2. **STEROID SPARING EFFECT OF ABATACEPT, MEASURED AS COMPARISON OF DAILY DOSE AT BASELINE AND 16 WEEKS AND AS CUMULATIVE GLUCOCORTICOID DOSE OVER THE 16 WEEKS PERIOD.**
3. **PROPORTION OF SUBJECTS WITH NO BILAG A IN ANY SYSTEM OTHER THAN MUSCULOSKELETAL AT 16 WEEKS.**
4. Proportion of subjects with no deterioration in physician global assessment at 16 weeks.
5. Comparison of fatigue at baseline and 16 weeks as measured by the FACIT
6. Comparison of quality of life at baseline and 16 weeks as measured by the SF 36
7. Safety, measured in standard methods as AE and SAE, inducing likelihood that the AE/SAE was related to the study biologic.
8. Time to  $\geq 20\%$  response, measured as joint counts (sum of tender and swollen joints) at baseline, 4, 8, 12 and 16 weeks.
9. Change in peripheral blood T cell compartments indicating decline in pro-inflammatory profiles, i.e. we expect decrease in CD4+ effector T cells that make IFNgamma (TH1) and IL-17 (TH17) and increase in ratio of Treg to Teff, as well as increased functions of the Tregs and decreased function of the helper T cells. CD4+CD25+ Foxp3 and CD8+Foxp3+ will be the definition of regulatory T cells. These will be measured at baseline and 16 weeks.
10. Change in anti-DNA and complement levels measured at zero, 8 and 16 weeks.

11. Change in BLyS levels from baseline to 16 weeks. We expect BLyS levels may rise as abatacept interferes with T cell action and thus with T cell help to B cells, with less B cell activation and less progression of B cells to short-lived plasma cells, and therefore a potential drop in B cell numbers and rise in BLyS levels. If this does not occur, then the effects of abatacept on B cells would be considered less dramatic than the effects of B cell depletion by rituximab.
12. Effects of treatment on extra-articular systems involved with SLE, such as skin, mucous membranes, serosal surfaces, systemic symptoms at baseline, 4, 8, 12 and 16 weeks.

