### **8.2 Populations for Analyses**

The study analyses will be performed at the termination of the study; once the last visit of the last patients has been recorded. The analyses will be performed on the 64 SLE patients enrolled in the study based on the inclusion and exclusion criteria as stated above.

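### The imputation rule in 8.4.3 names weeks 12 and 24, so it does not fit the week-16 endpoint, and it leaves out joint counts collected at weeks 4 and 8 and at early termination

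*Combined protocol and SAP*

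**What the plan says.** The primary efficacy measure in 6.4.1 is the proportion of patients with at least 20% "Improvement in tender and swollen joint counts at 16 weeks". In 6.4.2 the time-to-response endpoint is "measured as joint counts (sum of tender and swollen joints) at baseline, 4, 8, 12 and 16 weeks".

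For missing data, 8.4.3 plans multiple imputation for "missing data at 12 and 24 weeks due to patients lost to follow up". It describes the model in one sentence: "The imputation model will include all baseline 12 week and 24 week outcomes and covariates to impute the missing outcomes". It adds: "Analyses will be done with and without imputation". The covariates are not listed. The reference attached to the imputation sentence appears in the reference list as a rheumatoid arthritis efficacy trial, so its entry does not point to a fuller description of the method.

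Section 8.2 states: "The analyses will be performed on the 64 SLE patients enrolled in the study". The visit text in 6.1 makes week 24 a follow-up phone call. The schedule table gives that call no efficacy assessment, and it marks a 28-joint count at the early withdrawal visit.

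**The concern.** An imputation rule has to name the variable and time point to be filled in, and it should use what was observed on the patient up to departure. This rule does neither for the primary endpoint. Week 16 is absent, and one of its two post-baseline time points has no efficacy data.

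Two things are at stake. First, the analyst would have to devise the working model later, which leaves an open choice on the primary endpoint of a 64-patient trial. Second, a literal repair that only changes 24 to 16 would still ignore the week-4, week-8 and termination counts of a patient who leaves before week 12. Those counts are the best available evidence on how that patient's joints were doing.

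**Working it through.** **1. The rule against the schedule**

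| Time | Role in 8.4.3 | Joint count in 6.1 |
|---|---|---|
| Baseline | predictor | yes |
| Week 4 | not named | yes |
| Week 8 | not named | yes |
| Week 12 | imputed, and predictor | yes |
| Week 16 (primary) | not named | yes |
| Early termination | not named | yes |
| Week 24 | imputed, and predictor | no, phone call |

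Of the two post-baseline times named, only week 12 has a joint count. A patient who leaves after week 8 and before week 12 has neither named value, so the listed model holds only baseline outcomes and covariates for that patient. If 24 is changed to 16, the same patient still has only baseline outcomes.

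**2. How many patients**

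The plan's sample size reproduces. With 67% against 30%, two-sided 0.05, power 0.80, pooled variance and no continuity correction:

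- Mean rate = (0.67 + 0.30)/2 = 0.485.
- n = [1.960 × √(2 × 0.485 × 0.515) + 0.842 × √(0.67 × 0.33 + 0.30 × 0.70)]² / 0.37² = 27.4, so 28 per group.
- With 12% dropout: 28/0.88 = 31.8, so 32 per group. Completers: 64 × 0.88 = 56.3, so 56.

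Section 8.1 therefore implies 32 − 28 = 4 leavers per arm. The synopsis says "We expect 30 patients in each group to complete the 16 week study", which implies 32 − 30 = 2. Neither gives the timing, so the share leaving before week 12 is unknown.

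**3. What the interim counts could change (illustration, not a forecast)**

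Assumptions:

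- Arm is in the imputation model.
- Baseline is uninformative.
- The week-8 and week-16 states follow a bivariate normal with correlation 0.3, 0.5 or 0.7. The documents give no such correlation.
- The leaver is among the worst 12% of the arm at week 8.

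Imputed probability of response at week 16:

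| Correlation | Abatacept, week 8 ignored | Abatacept, week 8 used | Placebo, week 8 ignored | Placebo, week 8 used |
|---|---|---|---|---|
| 0.3 | 0.67 | 0.47 | 0.30 | 0.14 |
| 0.5 | 0.67 | 0.33 | 0.30 | 0.06 |
| 0.7 | 0.67 | 0.17 | 0.30 | 0.01 |

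One such abatacept leaver moves that arm's rate by 0.20/32 = 0.6 to 0.50/32 = 1.6 points. One such placebo leaver moves that rate by 0.16/32 = 0.5 to 0.29/32 = 0.9 points. On the treatment difference:

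- Two per arm: 2 × (0.20 − 0.16)/32 = 0.3 to 2 × (0.50 − 0.29)/32 = 1.3 points too high if week 8 is ignored.
- Four per arm: 0.5 to 2.6 points too high.
- Four on abatacept only: 4 × 0.20/32 = 2.5 to 4 × 0.50/32 = 6.3 points too high.
- Four on placebo only: 4 × 0.16/32 = 2.0 to 4 × 0.29/32 = 3.6 points too low.

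If leavers had improved by week 8, the signs would reverse. The assumed planning difference is 37 points.

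**The case against.** The strongest reply is that little depends on this. Imputation is an additional analysis, and results are also reported without it. If the 64 enrolled patients in 8.2 are read as a fixed denominator, a patient with no week-16 count simply has not achieved response, and the unimputed analysis needs no imputation model. The wrong weeks look clerical, and a competent statistician would put in week 16. The undefined covariates could include interim counts.

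Part of this stands. The unimputed analysis is untouched under the fixed-denominator reading, and the number of leavers is small. But 8.2 does not say that a missing value counts as non-response, so that reading is only one of those available. Nothing says the covariates include interim counts, and correcting the week number alone does not bring them in.

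A reader might also infer that a patient withdrawn at week 8 for worsening will be imputed with that worsening ignored. The documents do not support that:

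- Section 8.4.3 mentions only loss to follow-up. A patient whom the investigator withdraws, and who is due a completion visit within a week under 4.1, is not obviously lost.
- Under 4.2.3, "if significant worsening of disease activity is found at 8 weeks in comparison to baseline disease activity", the investigator only considers discontinuation. The criterion is disease activity, so the joint count need not show the worsening.
- Many such patients would already be failures under 4.1, through a new or increased drug or prednisone above 10 mg at or after week 8.

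**Conclusion.** The point holds. The rule is wrong as written for this trial because it omits the primary time point, names a time with no efficacy outcome, and leaves out joint counts already collected. For a patient who leaves before week 12 and is imputed, only baseline outcomes and unnamed covariates remain. This follows from the text and needs no assumption.

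The numerical effect is probably small and its direction is unknown. In the illustration it stays within 2.6 points on the difference when leavers are balanced. It is larger only if all four expected leavers in one arm, and none in the other, are among the worst at week 8. Those figures rest on assumed correlations, on arm being in the model, and on every leaver being both badly worsened and imputed, so they sit at the high end. The documents do not support a claim that the rule favours abatacept. Correcting it is worthwhile because it is cheap and removes an analyst's choice before unblinding.

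**What to change.** In 8.4.3, replace the reference to 12 and 24 weeks with week 16 and any earlier scheduled visit, and replace the model sentence with:

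> The imputation model will include treatment arm, site, the baseline covariates of the adjusted model, and all outcomes at baseline and weeks 4, 8, 12 and 16 where collected, including the 28-joint tender and swollen counts. An early-termination count is used at the scheduled visit whose window it falls in, otherwise as an auxiliary variable, and as the week-16 count only if within the Visit 5 window (+/-5 days). Missing week-16 values are imputed whatever the reason for missingness, unless the patient is already a treatment failure under 4.1.

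If the visit in that window already has its own count, the termination count should also go in as auxiliary. A count at day 63, for example, lies outside the week-8 window (days 51 to 61) and should not be placed at week 12. Counts outside every window will add little, since patients who have one usually have no week-16 value from which to learn the relation. Most of the gain comes from weeks 4, 8 and 12.

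Cost: slightly more analysis work, a somewhat larger imputation model for 64 patients, and a wording change that needs IRB/IEC approval under 9.1. No visit or measurement is added. Whether to score withdrawal for worsening as non-response is a separate, optional endpoint decision and is not part of this change.
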